**b. Protection Against Risk:**

*i. Risk of loss of confidentiality:* All information will be stored in locked files in a locked research area that can be accessed only by members of the research team. Computer files containing research information will be kept on the private research local area network (LAN) belonging to the PI. This LAN is not accessible to others outside the [name] lab. Files containing identifying information are password protected, and the computers are housed in the PI's lab. Only [name] research staff has keys that access this research area. No names or other identifying information will be used in publications that stem from this research. Under no circumstances will personally identifying information be released to any outside party (beyond those immediately connected with the study) without the written consent of the participant (or his/her guardian). There has been no breach of subject confidentiality from [name] lab in her 25 years of clinical research, so this risk is considered minimal.

*ii. Risk of emotional upset during interviewing:* The research assistants for the study, [name] and [name], are both highly experienced in conducting interviews and research interactions with participants with SCZ. If a participant becomes upset at the clinical material being discussed, [name], an extremely experienced psychiatrist, will be available to intervene clinically. Additionally, the study will be conducted in the same building in which the participants' VA clinicians practice, so that a multiplicity of clinicians will be ready at hand if a participant becomes unduly upset.

*iii. Risks associated with estimated  $VO_{2\text{max}}$  assessment and exercise training. Heart rate and blood pressure will change as a result of the  $VO_2$  assessment and during the exercise sessions. Because of these changes* there is a minimal risk of cardiac event. Although any exercise program carries the possibility of a cardiac event, we minimized this risk by requiring each participant to be cleared by a doctor. Importantly, exercise intensity will start out at low levels and increase as the participants tolerate. Participants will also be permitted to take breaks as needed if they experience discomfort, undue fatigue or shortness of breath, or any chest pain.

**Participants will not undergo exercise stress testing.** We considered adding an exercise stress test prior to randomization. An advantage of this would be that it would provide an additional opportunity to detect severe cardiac disease that might increase the risk of an acute event during our AE intervention. After extensive deliberations, our research team decided with unanimous vote that including an exercise stress was not necessary and would not add additional information for the study or protection to the human participants. This decision was based on the following considerations:

- The recommendations published in JAMA by Gill et al. (2000) advised that a screening protocol based on a simple cardiovascular reserve test, similar to the one we plan as described above is more suitable for screening adults than a protocol based on stress exercise testing.
- The American Heart Association (AHA) and the American College of Sports Medicine (ACSM) joint position statement advised that "apparently healthy persons of all ages and asymptomatic persons at increased risk may participate in moderate-intensity exercise without first undergoing a medical examination or a medically supervised, symptom-limited exercise test" (American College of Sports Medicine 1998).
- Participants with potential cardiac contraindications to the proposed exercise program will be identified and excluded by means of the screening process.
- Exercise will be conducted in a supervised environment as described below in interventions section.
- We have found that a maximal or near maximal exercise test on a treadmill is an unpleasant, if not frightening experience, for sedentary and unfit adults.
- Regular exercise and physical activity may actually reduce the overall risk of myocardial infarction and death among older persons, possibly through improvements in cardiac risk factors and overall fitness (American College of Sports Medicine 1998).

In summary, we concluded that exercise stress testing would provide little additional information, was not necessary to protect the safety of participants, and that it is disliked by sedentary and unfit participants. Our protocol for the AE intervention also requires that the sessions carefully monitored for cardiac and other signs and symptoms by trained staff. To date, we have enrolled nearly 100 older adults, with and without neurological disease, in various exercise interventions and have no adverse events related to cardiac symptomatology.

*iv. Risks associated with cognitive and functional performance testing:* The risks are minimal. If participants become frustrated, they will be permitted to take breaks from the assessments.

### **3. POTENTIAL BENEFIT OF THE PROPOSED RESEARCH TO THE PARTICIPANT AND OTHERS**

The risks of this study are minimal since the procedures are noninvasive and protections are in place to minimize risks (see above sections on risks). All participants will receive monetary compensation for their time and travel incurred as part of their participation. The study may lead to knowledge that AE is effective in enhancing outcomes in VA patients with SCZ. The VA system could ultimately be spared the burden of protracted and incomplete rehabilitation of many of our patients with SCZ. The patients themselves will be afforded a greater chance to lead more functional and satisfying lives. Hence this proposal is highly relevant to the VA mission of rehabilitation of our Veteran patients.

### **4. IMPORTANCE OF THE KNOWLEDGE TO BE GAINED**

Schizophrenia affects two to three million Americans, many of whom are Veterans. Schizophrenia is a very disabling disease with poorly understood etiology and pathophysiology. Persons suffering from this

disorder occupy one half of psychiatric beds in the U.S. and account for fully one third of VA inpatient days of care. Estimates of the cost of this illness have ranged from \$20 billion to \$48 billion annually. Our treatment of many of these Veterans with SCZ is protracted and of very limited success because many patients' symptoms are inadequately responsive to neuroleptics. The fact that currently available treatments leave many individuals with long-term disabilities and are ineffective in 20-30% of patients makes the advancement of our treatment of this disorder of urgent concern. Improvements in cognitive function and skills of everyday living are highly resistant to treatment with our currently available medications. The deficits in function seen in so many of our patients with schizophrenia create untold suffering for them and their families. Our study may lead to the adoption of computerized cognitive remediation as a way of enhancing outcomes in SCZ without incurring pharmacological risk.

## **5. DATA AND SAFETY MONITORING**

The study will be overseen by the Data and Safety Monitoring Board (DSMB) at Emory University in the Department of Psychiatry and Behavioral Sciences. A report will be submitted to that DSMB on an annual basis, and the results of DSMB review will be reviewed in turn by [name] and the study staff and filed with our IRB. Any safety problems will be addressed in consultation with our DSMB. Regarding data safety and integrity, the PI and study staff work closely with the R&D Service Line and the Research Integrity Officer and follow all recommendations to ensure data integrity. We take compliance extremely seriously, and all study staff participate fully in human subjects and research training both at the Atlanta VA and Emory University. We store hard copy study documents in locked file cabinets in a locked research area ([name] lab) to which only our research staff have keys. Computerized data are stored in a set of relational databases customized by [name] in Filemaker Pro. [name] will work collaboratively with [name] to customize databases for the specific data needs of this study. These databases are password protected, as are the computers our research staff use for access. The databases have data integrity checks built in. Only [name] lab research staff have keyed access to the [name] lab that houses these computers. The data is stored on a VA research drive that is managed by the IT service in concert with the R&D Service Line at the Atlanta VA. Our computer back-up procedures are thorough and include daily off-site back up as provided by an off-site VA server under management of the R&D Service Line.

## **5. VERTEBRATE ANIMALS - not applicable**

### Inclusion of Women and Minorities

Women have been included among our SCZ participants at approximately 10-15 percent. We will continue to strive to recruit female participants at a comparable rate. Minorities have been included among our participants at approximately 50 percent in the [name] lab SCZ projects to date. We will continue to strive to recruit minority participants at a comparable rate.

### Inclusion of Children

Children under the age of 18 may not be enrolled according to VA rules. Participants ages 18-21 will be included in numbers proportionate to their prevalence in the VA SCZ population. This proportion is steadily increasing as a result of the two current wars and the increase in young military recruits over the past few years.

**Targeted/Planned Enrollment Table**

This report format should NOT be used for data collection from study participants.

**Study Title: Cognitive Remediation Treatment for Severe Mental Illness**

**Total Planned Enrollment: 40**

TARGETED/PLANNED ENROLLMENT: Number of Subjects			
Ethnic Category	Sex/Gender		
	Females	Males	Total
Hispanic or Latino	0	1	1
Not Hispanic or Latino	5	34	39
Ethnic Category: Total of All Subjects *	5	35	40
Racial Categories			
American Indian/Alaska Native	0	1	1
Asian	0	1	1
Native Hawaiian or Other Pacific Islander	0	0	0
Black or African American	3	18	21
White	2	15	17
Racial Categories: Total of All Subjects *	5	35	40

\* The “Ethnic Category: Total of All Subjects” must be equal to the “Racial Categories: Total of All Subjects.”

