## **RESEARCH DESIGN AND METHODS**

**Study Design:** The study will be a randomized parallel group clinical trial to compare twelve weeks of AE with a control condition (stretching and balance training) in 40 participants with SCZ (20 per group).

**Description of study population:** Participants for the study will be 40 participants treated at our Atlanta VA with a diagnosis of SCZ. Diagnosis will be confirmed by chart review and by a structured diagnostic interview (Structured Clinical Interview for DSM-IV, SCID-Axis I, patient version). Inclusion/exclusion criteria will be evaluated by means of chart review and participant interview.

**Inclusion criteria:** (1) Diagnosis of SCZ; (2) male or female, ages 18-70; (3) maintained on stable doses of outpatient psychiatric medications for at least 30 days; (4) compliant with outpatient follow-up (defined as coming for at least 75% of outpatient appointments within the previous 12 months); (5) have a stable place to live; (6) access to transportation to the VA. Participants will be sedentary as defined by reporting <20 min/week of performing regular physical activity in the past month.

**Exclusion criteria:** (1) Bipolar disorder;

- Criteria to rule out participants unlikely to be able to comply with treatment schedule: (2) active substance dependence within the prior 30 days; (3) more than 2 psychiatric admissions within the prior six months
- Criteria to rule out participants unlikely to be able to benefit from treatment: (4) known HIV infection or AIDS; (5) history of traumatic brain injury; (6) seizure disorder; (7) known Alzheimer's disease or other dementia; (8) clinical history of mild cognitive impairment (MCI); (9) Parkinson's disease; (10) other current clinically significant neurological disease, (11) unstable medical condition that would be expected to interfere with fitness training; (11) significant hearing or visual impairment.

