## Sample size determination

Sample size calculations for our primary outcome measure (MCCB) are based on several studies of AE compared to a control condition in which the effect sizes average approximately 0.5 (Dustman et al. 1984; Fabre et al. 2002; Heyn et al 2004; Hotting et al. 2012; Chapman et al. 2013). We also based estimated power on studies of cognitive remediation in SCZ, including a meta-analysis (Wykes et al. 2011) and studies of Posit Science computerized remediation (Fisher et al. 2010). The average effect size of the above studies is 0.5. With alpha set at 0.05, an effect size of 0.5 will yield a power of 0.80 for our **planned sample size of 20 completers per treatment group (with dropouts replaced)**. This sample size will be adequate to detect significant between group differences in MCCB change scores. More importantly for a pilot study, this sample size will allow us to estimate effect sizes specific to the target Veteran population with sufficient confidence to be useful in determining the sample size required for a future full Merit Review proposal (if indicated by the results of this pilot study). Participant retention will be an important issue. We estimate liberally from our prior work (cognitive remediation study) that *dropouts will be approximately 25%, so we will need to recruit 53 subjects in order to obtain the 40 completers needed for analysis.*

**Roles of members of the research team.** Please see delineation of roles in Budget Justification.

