## 1. RISKS TO SUBJECTS

### a. Human Subject Involvement and Characteristics:

Inclusion/exclusion criteria will be assessed for each participant by means of computerized chart review as well as participant interview and, where applicable, discussion with the participants' VA clinician.

*i. Participants with SCZ.* We will recruit 40 male and female participants with SCZ, aged 18-70. A diagnosis of SCZ, any subtype, will be confirmed by SCID. Inclusion criteria will be: (1) Diagnosis of SCZ; (2) male or female, ages 18-70; (3) maintained on stable doses of outpatient psychiatric medications for at least 30 days; (4) compliant with outpatient follow-up (defined as coming for at least 75% of outpatient appointments within the previous 12 months); (5) must have a stable place to live; (6) access to transportation to the VA. The participants will receive a psychiatric and medical history and be excluded if they have: (1) Bipolar disorder; (2) active substance dependence within the prior 30 days; (3) more than 2 psychiatry admissions within the prior six months, (4) known HIV infection or AIDS; (5) history of traumatic brain injury; (6) seizure disorder; (7) known Alzheimer's Disease or other dementia; (8) clinical history of mild cognitive impairment (MCI); (9) Parkinson's Disease; (10) unstable medical condition that would be expected to impair attention; (11) hearing impairment; (12) visual impairment (worse than corrected 20/40 by eye chart screening).

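### The human-subjects section and enrolment table give 40 as the number recruited, but 40 is the completer target; the sample-size section needs 53 recruited

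*Combined protocol and SAP*

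**What the plan says.** Four places give a number of participants.

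- **Research Design and Methods, Study Design:** the comparison is made "in 40 participants with SCZ (20 per group"). It does not say whether these are people enrolled or people completing.
- **Sample size determination:** the target is a "planned sample size of 20 completers per treatment group (with dropouts replaced"). It expects that "dropouts will be approximately 25" percent, "so we will need to recruit 53 subjects in order to obtain the 40 completers needed for analysis".
- **Risks to Subjects, Human Subject Involvement and Characteristics:** "We will recruit 40 male and female participants with SCZ, aged 18-70".
- **Targeted/Planned Enrollment Table:** "Total Planned Enrollment: 40". The sex, ethnicity and race totals each come to 40.

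The Statistical analysis plan, Specific Aim 1, ties its sensitivity statement (f = 0.456, alpha 0.05, power 0.80) to 20 completers per group.

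**The concern.** The sample-size section and the human-subjects section both describe how many people will be recruited, and they give 53 and 40. The enrolment table sides with 40. Neither the human-subjects section nor the table mentions completers, dropout or replacement, so a reader who starts there would take 40 as the intake.

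The difference matters because the Aim 1 power statement is conditional on 40 people finishing. Replacing dropouts means enrolling more than 40, and the two sections that state enrolment make no room for it. If whoever oversees recruitment works from those sections, the trial would stop short of the sample that its primary comparison assumes. The demographic table would also describe about 13 fewer people than the sample-size section expects to enrol (53 − 40 = 13).

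**Working it through.** **Inputs.** Completers needed: 40, 20 per group (Sample size determination; SAP, Specific Aim 1). Dropout: about 25% (Sample size determination). Aim 1 effect: f = 0.456, alpha 0.05, power 0.80 (SAP, Specific Aim 1). Covariates: baseline score, age, sex and anticholinergic load, so four (same place). Alternative retention: 82.5% for the exercise laboratory (Potential challenges; Preliminary Studies gives the same figure as attendance), and 83% or 85% for the earlier cognitive training study (Potential challenges; Preliminary Studies). The sidedness of the test is not stated; two-sided is assumed.

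**1. The plan's recruitment figure.** Recruits = completers ÷ (1 − dropout) = 40 ÷ 0.75 = 53.3. The stated 53 reproduces, and 53 × 0.75 = 39.75 expected completers. With a dropout rate given only as approximate, 53 against 54 is rounding.

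**2. The plan's power figure.** For a two-group ANCOVA with N completers and four covariates, the test statistic is F with 1 and N − 6 degrees of freedom and noncentrality λ = f² × N. At N = 40, λ = 0.456² × 40 = 8.32 with 34 denominator degrees of freedom, and power is 0.800. A two-sample t-test gives 0.8025. The statement therefore reproduces with 40 completers and a two-sided test; one-sided, the t-test would give 0.88.

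**3. If 40 were the enrolment limit.** Completers = 40 × retention: 40 × 0.75 = 30; 40 × 0.825 = 33; 40 × 0.85 = 34.

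| Completers | λ at f = 0.456 | Power (ANCOVA, 4 covariates) | f detectable at 80% power |
|---|---|---|---|
| 40 | 8.32 | 0.80 | 0.456 |
| 34 | 7.07 | 0.73 | 0.50 |
| 33 | 6.86 | 0.71 | 0.51 |
| 30 | 6.24 | 0.67 | 0.53 |

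The t-test without covariates gives nearly the same result at 30 completers: power 0.674 and detectable f = 0.530. As a standardised mean difference (d = 2f), the detectable effect rises from 0.91 to about 1.06.

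**4. What this check does not cover.** The sample-size section separately claims that "an effect size of 0.5 will yield a power of 0.80" with 20 completers per group. Read as a standardised mean difference, 0.5 gives two-sided power of 0.34 with 20 per group and 0.26 with 15. Read as f = 0.5, it gives 0.87 with 40 completers and 0.75 with 30. The metric is not stated. The loss shown in step 3 is therefore measured against the Aim 1 statement only.

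**The case against.** The best defence is that the sample-size section is the operative text and it is clear: 20 completers per group, dropouts replaced, 53 to be recruited. The opening aims and the study design paragraph use 40 as the design number, and the other two sections have probably just repeated it. Nothing calls 40 a ceiling. That stands. A reader might infer from the enrolment table that the trial will finish with about 30 completers and miss its power; the documents do not support that, because they plan to replace dropouts. The defence explains the likely intent but does not remove the contradiction, since replacement needs an enrolment above the figure that the human-subjects section and the table state.

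Three further limits also stand.

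- The plan calls its 25% dropout a liberal estimate, and the other retention rates it quotes give a smaller loss. A range is fairer than the single figure of 0.67.
- A reader might treat 53 as an arithmetic error for 54. It is not a useful correction. With a fixed intake at 25% dropout, the chance of at least 40 completers is about 54% with 53 enrolled and 63% with 54. Writing a cap of 54 would itself restrict the replacement that the plan relies on.
- A reader might infer that safety projections are understated too. The risk and monitoring sections contain no numerical safety projection tied to 40; only the demographic table is affected.

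The pilot also puts effect-size estimation ahead of testing, which softens the consequence. Aim 1 is nevertheless stated as a hypothesis test with a power figure.

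**Conclusion.** The contradiction is real: recruitment is 40 in the human-subjects section and the enrolment table, and 53 in the sample-size section. The 40 is the completer target. The stated Aim 1 power of 0.80 at f = 0.456 holds for 40 completers and not for 40 enrolled.

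The size of the harm is conditional on 40 being applied as the limit on enrolment. In that case power would be about 0.67 at 25% dropout, or 0.71–0.73 at 82.5–85% retention. This assumes a two-sided test at 0.05, four covariates and roughly equal dropout between the groups. If recruitment follows the sample-size section, the Aim 1 power is unaffected and the error is one of labelling, in the sections that state enrolment. Reconciling the numbers does not settle the separate claim of 0.80 power at an effect size of 0.5.

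**What to change.** 1. In the Study Design paragraph, the human-subjects section and the enrolment table, give the two numbers separately: about 53 enrolled, with dropouts replaced until 40 complete (20 per group).
2. Rebuild the enrolment table for the enrolled number. Check its source first: it is headed with the title of a cognitive remediation study, so its rows may have been carried over from another application and should not simply be scaled up.
3. If 40 really is the enrolment limit, say so in the sample-size section, remove the statements on replacement and on recruiting 53, and restate the Aim 1 power and detectable effect for about 30 to 34 completers (power 0.67–0.73 at f = 0.456; f about 0.50–0.53 at 80% power).

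The first two changes cost wording and one table, with no change to the design, since the plan already intends to recruit more than 40.
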